## 6. PROCEDURES

Any questions regarding the protocol should be directed to the Celgene Medical Monitor or designee.

# **6.1.** Screening Period

The Screening Phase begins when the ICF is signed. Screening evaluations will be performed for all subjects to determine study eligibility. These evaluations must be completed within 28 days of first dosing unless noted otherwise below.

Waivers to the protocol will not be granted during the conduct of this trial, under any circumstances.

Except for pregnancy tests, ECGs and urinalysis, all safety-related laboratory assessments will be performed centrally; however, tests that may result in dose interruption and/or modification may also be performed locally to allow for treatment-related decisions during subject visits. All results from local laboratories used in treatment decisions or AE reporting must be entered as an unscheduled visit into the electronic case report form (eCRF).

The following will be performed at screening as specified in Table 4 after informed consent has been obtained:

- Interactive Response Technology (IRT) registration
  - Note: Subject may be enrolled in the IRT up to 3 days prior to initiating study treatment on Cycle 1 Day 1 (C1D1)
- Complete medical history (all relevant medical conditions diagnosed/occurring prior to screening should also be included)
- Demographics (age, sex, race, and if allowed by local regulations, ethnicity, and date of birth, will be collected in the eCRF and/or IRT system)
- Prior disease history (if available the date of initial diagnosis, staging at time of diagnosis [Appendix D], cytogenetics at diagnosis to be collected)
- Prior disease therapies (including surgery, radiation, systemic or any other therapy for the subject's disease)
- Prior and concomitant medication evaluation (including those taken ≤ 28 days before the date that the ICF was signed, except for those taken for disease)
- Prior and concomitant procedures evaluation (including all procedures occurring ≤ 28 days before the date that the ICF was signed)
- Adverse events
- Physical examination, including assessment for potential venous thromboembolism events (VTEs) (can be source documented only)
- Forced expiratory volume test (subjects with or suspected to have chronic obstructive pulmonary disease [COPD])

- Vital signs (including blood pressure, temperature, and heart rate)
- Height and weight
- 12-lead ECG (performed and reviewed locally)
- Hepatitis panel
- HIV-1 antibody test
- Hematology panel including complete blood count (CBC) with differential, including red blood cell (RBC) count, hemoglobin, hematocrit, white blood cell (WBC) count (with differential), platelet count, mean corpuscular volume
- Coagulation parameters (prothrombin time/international normalized ratio, activated partial thromboplastin time, fibrinogen)
- Chemistry panel including sodium, potassium, calcium, corrected serum calcium (refer to Section 6.4.1), chloride, blood urea nitrogen (BUN), creatinine, glucose, albumin, total protein, alkaline phosphatase (ALP), bilirubin (total, direct, and indirect), AST, ALT, lactate dehydrogenase (LDH), magnesium, bicarbonate, lipase, gamma-glutamyl transferase (GGT), uric acid, triglycerides, cholesterol, and amylase. (NOTE: Tests for AST, ALT, ALP, direct bilirubin, indirect bilirubin, and total bilirubin must be conducted and assessed concurrently)
- Thyroid function tests (thyroid-stimulating hormone [TSH], free T4, free T3)
- Estimation of renal function will be assessed using the CrCl calculated based on the Cockcroft-Gault formula or the CrCl directly calculated from the 24-hour urine collection method. Cockcroft-Gault formula: CrCl (mL/min) = (140 age) (weight [kg]) / 72 (serum creatinine [mg/dl]); for females, the formula is multiplied by 0.85.
- Urinalysis (color, appearance, specific gravity, pH, protein, glucose, ketones, blood, bilirubin)
- Females of childbearing potential (FCBP) should have two negative medically supervised pregnancy tests assessed locally during screening. The subject may not receive any study treatment until the investigator has verified that the results of these pregnancy tests are negative.
  - The investigator will appraise a female subject as a FCBP according to the following definition (justification must be recorded in the eCRF and the source document):
    - FCBP is defined as a sexually mature woman who has not undergone a hysterectomy or bilateral oopherectomy or has not been naturally menopausal for at least 24 consecutive months (ie has had menses at any time in the preceding 24 consecutive months). Amenorrhea following cancer therapy does not rule out childbearing potential.
  - o Negative serum pregnancy test (minimum sensitivity of 25mIU/ml) at screening
  - Negative serum or urine pregnancy test (investigator's discretion) within 72 hours prior to the start of study treatment (C1D1)

- Note: Pregnancy testing does not need to be repeated prior to C1D1 if the screening assessment (serum pregnancy test) was performed within 72 hours of the first dose of study treatment
- Note: Pregnancy testing is not required for non-FCBP subjects.
- Eastern Cooperative Oncology Group (ECOG) Performance Status (see Appendix C)
- Efficacy assessments / tumor evaluations per the IMWG criteria (See Section 6.4).
- β2 microglobulin test
- Bone marrow aspiration/biopsy (for cytogenetics, percent plasma cells,

# S, CCI

## **6.2.** Treatment Period

The subject will begin the treatment period upon confirmation of eligibility. The subject must start treatment within 28 days of signing the ICF. For all visits an administrative window of  $\pm$  3 days is permitted. Safety laboratory testing at a local laboratory may be performed up to 3 days before the study treatment administration day. Results of these laboratory tests must be evaluated before each study treatment administration.

Treatment cycles are 28 days in duration, the treatment and schedule will be as described in Section 7.2.

The following evaluations will be performed at the frequency specified in Table 4. The evaluations should be should be performed prior to dosing on the visit day, unless otherwise specified.

- Interactive Response Technology (IRT) registration
- Concomitant medications evaluation
- Concomitant procedures evaluation
- Adverse event (continuously)
- Physical examination, including assessment for potential VTEs (can be source documented only)
- Vital signs
- Weight
- 12-lead ECG (C1D1 and C6D1 immediately after DARA infusion)
- Blood Type, Rh, and indirect antiglobulin test (IAT) should be done before the first dose of DARA. See Section 6.8 for additional details.
- Hematology panel
- Coagulation parameters
- Chemistry panel

- Thyroid function tests:
  - Cycles 1 to 4: TSH, free T4, free T3
  - Cycle 5 onward: TSH, if TSH is abnormal, then reflex testing for free T4 and free T3
- Renal function (CrCl) based on the Cockcroft-Gault formula or the CrCl directly calculated from the 24 hour urine collection method. Cockcroft-Gault formula: CrCl (mL/min) = (140 age) (weight [kg]) / 72 (serum creatinine [mg/dl]); for females, the formula is multiplied by 0.85 (local laboratory).
- Urinalysis (only if clinically indicated)
- Urine (or serum) pregnancy test for FCBP (negative results required for study treatment [DURVA and/or DARA] administration) within 72 hours prior to dosing on D1 of every treatment cycle. The subject may not receive study treatment until the investigator has verified that the result of the pregnancy test is negative.
- ECOG Performance Status
- Antiviral prophylaxis
- Pre and post medication for DARA infusion (see Section 7.2.1.2)
- Efficacy assessments (see Section 6.4)
- β2 microglobulin test on Day 1 of each cycle
- CCI
- Blood sampling for PK assessments (see Section 6.5)
- CCI
- Study treatment (DARA and DURVA) administration/accountability/compliance.

## **6.2.1.** End of Treatment

An End of Treatment (EOT) evaluation will be performed for subjects who are withdrawn from treatment for any reason within 7 days after the decision to permanently discontinue treatment has been made.

The following evaluations will be performed as specified in Table 4.

- IRT registration
- Concomitant medications evaluation (monitored until 90 days after last dose of DURVA or DARA, whichever is later)
- Concomitant procedures evaluation (monitored until 90 days after last dose of DURVA or DARA, whichever is later)
- Adverse event evaluation (monitored until 90 days after last dose of DURVA or DARA, whichever is later)

- Physical examination, including assessment for potential VTEs (can be source documented only)
- Vital signs
- Weight
- 12-lead ECG
- Hematology panel
- Coagulation parameters
- Chemistry panel
- Thyroid function tests (TSH, free T4, free T3)
- Renal function (CrCl) based on the Cockcroft-Gault formula or the CrCl directly calculated from the 24 hour urine collection method. Cockcroft-Gault formula: CrCl (mL/min) = (140 age) (weight [kg]) / 72 (serum creatinine [mg/dl]); for females, the formula is multiplied by 0.85.
- Urinalysis
- Urine (or serum) pregnancy test for FCBP
- ECOG Performance Status
- Antiviral prophylaxis
- Efficacy assessments per the IMWG criteria will be performed according to the schedule defined in the Table of Events and do not need to be performed specifically for the EOT visit except as specified in Section 6.4.
- β2 microglobulin test
- CCI
- Blood sampling for DARA PK assessments (see Section 6.5)
- Study treatment (DARA and DURVA) accountability/compliance.

# 6.3. Follow-up Period

# 6.3.1. Safety Follow-up

All subjects will be followed for 90 days after the last dose of DURVA or DARA, whichever is later, for AEs, including adverse events of special interest (AESIs), reporting, as well as serious adverse events (SAEs) that had occurred within that time frame but were made known to the investigator at any time thereafter that are suspected of being related to study treatment (DURVA, DARA), as described in Section 10.1.

Subjects are to return to the study site 28 (+3) days after the EOT visit and 90 (+3) days after the last dose of DARA or DURVA, whichever is later, for safety follow-up visits procedures as specified in Table 4.

- Concomitant medications evaluation (monitored until 90 days after last dose of DURVA or DARA, whichever is later)
- Concomitant procedures evaluation (monitored until 90 days after last dose of DURVA or DARA, whichever is later)
- Adverse event (including AESIs) evaluation (monitored until 90 days after last dose of DURVA or DARA, whichever is later)
- Vital signs
- Weight
- Hematology panel
- Chemistry panel
- Thyroid function tests (TSH, free T4, free T3)
- Renal function (CrCl) based on the Cockcroft-Gault formula or the CrCl directly calculated from the 24 hour urine collection method. Cockcroft-Gault formula: CrCl (mL/min) = (140 age) (weight [kg]) / 72 (serum creatinine [mg/dl]); for females, the formula is multiplied by 0.85 (local laboratory).
- Urinalysis
- Urine (or serum) pregnancy test for FCBP
- Antiviral prophylaxis
- Blood sampling for DARA PK assessments (see Section 6.5)
- CC

# **6.4.** Efficacy Assessments

# 6.4.1. Laboratory Assessments for Efficacy Parameters

All laboratory assessments for efficacy will be performed centrally.

If screening assessments are performed within 3 days of C1D1, efficacy laboratory assessments need not be repeated at C1D1:

- Serum protein electrophoresis (sPEP) and urine protein electrophoresis (uPEP) tests (performed on 24-hour urine collection) are required at screening, on Day 1 of each cycle, and at the EOT Visit.
- Serum and urine immunofixation tests are required at screening, on Day 1 of each cycle, and at the EOT Visit.

- Quantitative serum immunoglobulin assessment includes IgG, IgA, and IgM for all subjects, and IgE or IgD only for subjects with the respective MM subtype (IgE or IgD) and is required at screening, on Day 1 of each cycle, and at the EOT Visit.
- Serum free light chains assay is required at screening, on Day 1 of each cycle, and at the EOT Visit.
- Corrected serum calcium will be assessed as part of the safety serum chemistry assessments performed at screening, on Day 1 of each cycle, and at the EOT Visit.

# 6.4.2. Bone Marrow Aspiration and/or Biopsy

A bone marrow aspirate (BMA) and biopsy (BMB) is mandatory at the following time points:

- At screening, BMA and BMB for percent plasma cells, cytogenetics,
- During treatment:
  - \_ CCI
  - BMA and BMB at the time of complete response (CR) confirmation for percent plasma cells
  - \_ CCI

The analysis of bone marrow for percentage of plasma cells will be performed locally and at a central laboratory.

#### 6.4.3. Bone Lesion Assessment

Bone lesion assessment by x-ray (skeletal survey) or CT Scan will be performed at screening and when clinically indicated to confirm response or PD. The same method (x-ray or CT Scan) should be used throughout the study. All films will be analyzed locally by the site investigator/radiologist. If a bone lesion assessment by x-ray or CT Scan was performed within 60 days prior to the start of Cycle 1, it may be used for the screening assessment.

If assessment is done by x-ray, the following are the minimum plain radiological films required for the skeletal (bone) survey:

- Lateral skull
- Anteroposterior (AP) and lateral cervical spine
- AP and lateral thoracic spine
- AP and lateral lumbar spine
- Posteroanterior chest
- AP pelvis
- AP upper extremities, shoulder to elbow

• AP lower extremities, hip to knee.

Other radiological films may be necessary to view symptomatic areas or known pre-existing lesions in skeletal regions not included in the films above.

## **6.4.4.** Extramedullary Plasmacytoma Assessments

Clinical assessment for extramedullary plasmacytoma (EMP) assessments will be performed at screening, on Day 1 of every cycle, and at the EOT Visit.

For EMPs that are only assessable radiographically (by x-ray and/or conventional [spiral] CT/magnetic resonance imaging [MRI] scan), scans are required at screening, at Cycle 3 Day 1, every 3 cycles thereafter (Cycle 6 Day 1, Cycle 9 Day 1, etc.) during treatment, at the EOT Visit, and when clinically indicated to confirm a response (≥ PR) or PD. The radiographic modality used at screening (eg, x-ray) will be repeated at each assessment time point throughout the study. All scans will be reviewed locally only. Celgene may request redacted copies of reports.

# **6.4.5.** Assessment of Response

## **6.4.5.1.** Investigator Assessment

Starting from Cycle 2, response will be assessed by the investigators using the International Myeloma Working Group (IMWG) Uniform Response Criteria (Rajkumar, 2011) (Appendix B) at every cycle on Day 1 and at the EOT Visit. Response must be based on the central laboratory data to ensure consistency across investigative sites. All treatment discontinuation decisions due to disease progression will be made by treating physicians based on response as assessed using results from central laboratories by the IMWG criteria, except for new or increase in bone lesions or soft tissue plasmacytomas.

## 6.4.5.2. Independent Response Adjudication Committee Assessment

An IRAC will be formed by a group of experts in the MM disease area to review efficacy data. For each subject, the IRAC will determine tumor response at scheduled or unscheduled visits, and the time of PD (if disease progressed). In addition, the IRAC will determine the best overall response of each subject up to time of the data cut off for interim and final analyses.

The IRAC will adjudicate efficacy data incrementally according to IRAC Charter during the study. The IRAC adjudicated response data will be used for efficacy analysis in all interim and final analyses. Primary efficacy analyses will be conducted in tumor response data, including progressive disease (PD) that are assessed by the IRAC according to the IMWG Uniform Response Criteria (Appendix B).

NOTE: Per IMWG Uniform Response Criteria all response categories and progressive disease require 2 consecutive assessments except for radiographic or bone marrow assessments

### 6.5. Pharmacokinetics

Serum samples will be collected to assay concentrations of DURVA and DARA. On PK sampling days, dosing and sample collection information including dosing date, dosing time (24 hour clock), and actual PK blood sampling time (24 hour clock) should be accurately documented on the appropriate eCRF pages.

#### 6.5.1. Pharmacokinetics of Durvalumab

All subjects enrolled in Part 1 Stage 1 will participate in the DURVA PK sample collections at the following time points:

[figure not shown]
- C1D2: pre dose (-30 to -5 minutes prior to dose), end of infusion (EOI) (+5 minutes),
- C1D8: 144 hours post C1D2 dose (± 1 hour)
- C1D15: 312 hours post C1D2 dose ( $\pm$  1 hour),
- C1D22: 480 hours post C1D2 dose ( $\pm$  1 hour).
- Additional DURVA PK samples to be collected on C2D1, C4D1, C6D1, C10D1, and C14D1.

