#### 6.5.2. Pharmacokinetics of Daratumumab

DARA PK sample collections will occur at the following time points for subjects enrolled in Part 1 Stage 1:

- C1D1: predose (-30 to -5 minutes prior to dose), and EOI (+5 minutes)
- C1D8: predose (-30 to -5 minutes prior to dose), and EOI (+5 minutes)
- C1D15: predose (-30 to -5 minutes prior to dose), and EOI (+5 minutes)
- C1D22: predose (-30 to -5 minutes prior to dose), and EOI (+5 minutes)
- EOT
- 28 days after EOT,
- 90 days after last DARA or DURVA dose

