#### 7.2.2. Treatment Schedule

### 7.2.2.1. Daratumumab Plus Durvalumab Treatment Schedule

See Section 3.1 for dosing rules.

- Intravenous DARA on the same dosing schedule received on last MM Daracontaining regimen
  - 16 mg/kg starting at the same dosing schedule; QW, Q2W, or Q4W, as their last DARA-containing MM therapy.
  - Dosing schedule should be adjusted as shown below; provided that the patient has a response of stable disease (SD) or better:
    - QW frequency (Days 1, 8, 15 and 22/28-day cycle): Weeks 1 to 8 then Q2W Weeks 9 to 24
    - Q2W frequency(Days 1, 15 of a 28-day cycle): Weeks 1 to 16 then Q4W
    - Q4W frequency (Day 1 of each 28-day cycle): Week 1 onwards until disease progression
- Intravenous DURVA:
  - 1500 mg on Day 2 of Cycle 1, then Day 1 of Cycle ≥ 2 of a 28-day cycle.

NOTE: For all DURVA infusions after Cycle 1, a+1 day window is allowed (subject may either receive the DURVA infusion on same day as the DARA infusion or on the next day per the investigator's discretion; concomitant administration of DARA and DURVA is prohibited).

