# 7.2.4. **Dose Modifications and Interruptions**

Subjects will be evaluated for AEs at each visit with the NCI CTCAE Version 4.03 or higher as a guide for the grading of severity.

If the treatment has been interrupted and the next cycle is delayed beyond Day 28 of the prior cycle, then Day 1 of the next cycle will be defined as the first day that study treatment is resumed

- If DURVA is permanently discontinued, then the subject must be permanently discontinued from all study treatments.
- If DARA is withheld or permanently discontinued, then DURVA dosing may be continued.

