11.8. Pharmacokinetic Analysis

Pharmacokinetic analysis will be based on the PK population. Non-compartmental PK parameters such as time to maximum concentration (T_{max}), maximum observed concentration (C_{max}), area under the curve (AUC), terminal elimination half-life (t_{1/2}), clearance (CL/F), and volume of distribution (V_z/F) will be estimated from the plasma concentration-time profile for DURVA. For DARA, typical serum PK parameters, such as C_{max}, AUC, T_{max}, t_{1/2}, CL/F and V_z/F will be summarized. All concentration data and PK parameters will be summarized descriptively.

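### If the durvalumab half-life is longer than about 11 days, the Cycle 1 profile is thin support for individual t1/2 and Vz; assaying serum already drawn for daratumumab would be a cheap improvement

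*Protocol*

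**What the plan says.** Durvalumab pharmacokinetics is a secondary endpoint (Protocol Table 2, SAP Table 3). SAP Section 11.8 says that Tmax, Cmax, AUC, t1/2, CL/F and Vz/F "will be estimated from the plasma concentration-time profile for DURVA" by a noncompartmental method. Protocol Section 9.9.1 gives the same list.

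On sampling, Protocol Section 6.5.1 says "All subjects enrolled in Part 1 Stage 1 will participate in the DURVA PK sample collections". In Cycle 1 the samples are pre-dose and end of infusion on Day 2, then 144, 312 and 480 hours after that dose. The section closes with "Additional DURVA PK samples to be collected on C2D1, C4D1, C6D1, C10D1, and C14D1". It does not say whether those later samples are pre-dose. Section 6.2 sets a general default that evaluations precede dosing on the visit day unless otherwise specified, and its list includes PK blood.

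For daratumumab, Section 6.5.2 adds samples from the same Stage 1 subjects at end of treatment (EOT), 28 days after EOT, and "90 days after last DARA or DURVA dose". In Table 4 the daratumumab PK row is marked at those three visits and the durvalumab row has dashes. The procedure lists in Sections 6.2.1 and 6.3.1 name daratumumab PK only.

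Section 7.2.4 adds: "If DURVA is permanently discontinued, then the subject must be permanently discontinued from all study treatments".

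**The concern.** A noncompartmental terminal half-life needs a declining profile long enough to show the terminal slope. CL is dose divided by AUC to infinity, and Vz is CL divided by the slope, so both inherit any error in the extrapolated tail. For durvalumab the next dose cuts the profile off after one cycle, and one sample per later cycle gives neither a slope nor an interval AUC. All three parameters must therefore come from Cycle 1.

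Meanwhile serum is drawn from the same subjects at three visits after treatment has ended, and only daratumumab is scheduled to be measured in it. Because stopping durvalumab ends all study treatment, those visits always follow the last durvalumab dose, which is where a terminal slope is best seen. At stake is whether the reported individual t1/2 and Vz mean much, and whether a reader could tell: the readable PK analysis sections give no minimum profile length and no limit on extrapolation.

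**Working it through.** **Length of the profile.** Inputs: dosing is "1500 mg on Day 2 of Cycle 1, then Day 1 of Cycle ≥ 2 of a 28-day cycle" (Section 7.2.2.1), and "Treatment cycles are 28 days in duration" (Section 6.2). Hours after the first dose = (study day − 2) × 24.

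- Day 8: 6 × 24 = 144; Day 15: 13 × 24 = 312; Day 22: 20 × 24 = 480. These reproduce the times in Section 6.5.1.
- C2D1 is study Day 29: 27 × 24 = 648 hours, or 27 days.

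The profile is 27 days if C2D1 is pre-dose (24 to 30 with the ±3-day visit window), otherwise 20 days. The terminal fit runs from day 6 to day 27 (21 days) or from day 6 to day 20 (14 days).

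**Extrapolated AUC and span.** The documents give no durvalumab half-life, so it is varied. For a one-exponential decline the share of AUC to infinity beyond the last sample at T days is 2^(−T/t1/2).

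| Assumed t1/2 (days) | Beyond day 27 | Beyond day 20 | 21-day fit, in half-lives |
|---|---|---|---|
| 7 | 7% | 14% | 3.0 |
| 10 | 15% | 25% | 2.1 |
| 14 | 26% | 37% | 1.5 |
| 18 | 35% | 46% | 1.2 |
| 21 | 41% | 52% | 1.0 |

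Two conventional limits, neither of them in the documents, are at most 20% extrapolated and a fit over at least 2 half-lives.

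- 27 days: t1/2 ≤ 27 × ln 2 / ln 5 = 11.6 days for the first; t1/2 ≤ 21/2 = 10.5 days for the second.
- 20 days: 20 × ln 2 / ln 5 = 8.6 days; 14/2 = 7.0 days.

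**Precision of one subject's t1/2.** Simulation with one exponential and 15% random error per sample; 5th to 95th percentiles:

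| True t1/2 (days) | Cycle 1, days 6, 13, 20, 27 | Post-treatment, days 30, 60, 90 |
|---|---|---|
| 10 | 8.2–12.9 | 9.2–10.9 |
| 18 | about 13–30 | 15.6–21.2 |
| 21 | about 14–40 | 17.9–25.5 |

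**Bias, and which parameters suffer.** A second simulation used two compartments (assumed distribution half-life 2 days carrying half the initial concentration, 20% error) and the 27-day profile:

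- True t1/2 of 18 days: median estimate 15.4 (10.4–29.0); median extrapolation 28%; 83% of profiles above 20%. Ratio to truth for Vz 0.87 (0.62–1.28), for CL 1.00 (0.74–1.22).
- True t1/2 of 14 days: median extrapolation 20%; 52% of profiles above 20%.
- True t1/2 of 10 days: median estimate 9.0 (7.1–12.3); median extrapolation 11%; 4% of profiles above 20%.

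With samples out to day 90 after a single dose, the range at 18 days narrows to 15.4–21.8 and median extrapolation falls to 3%.

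**The case against.** A reader might infer that the trial will report t1/2, CL and Vz that its samples cannot support. The documents do not carry that. They give no half-life; with a 27-day profile and a half-life of 7 to 10 days, both conventional limits are met. Nor do the three parameters fail together: at a true 18 days CL is unbiased at the median in the two-compartment simulation, while t1/2 and Vz are not.

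Other points on that side:

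- **Group summaries are less noisy than one subject's estimate.** PK parameters are to be summarised descriptively. In the one-exponential simulation the median of 18 subjects ranges from about 16 to 20 days at a true 18. This stands for random measurement error only. The downward bias in the two-compartment case would not average out.
- **Samples already scheduled could do much of the work.** A model fitted to Cycle 1 plus the C4, C6, C10 and C14 troughs gives about 15.5 to 21 days for one subject at a true 18, close to the post-treatment result; with C4 and C6 only, about 15 to 22. This stands, but the method that can be read is noncompartmental and cannot use those troughs for t1/2. Subjects who progress early will also lack the later ones.
- **Post-treatment timing will not be day 30, 60 and 90.** EOT follows the decision to stop, at any point in a cycle, and the last visit is timed from the later of the two drugs. This stands, and is why actual times are needed. The gain is not fragile: days 7, 35 and 90 give about 16 to 20 days at a true 18.
- **Redaction.** Parts of the PK text are blacked out and a figure in Section 6.5.1 is not shown, so a model-based analysis may exist. The sampling gap itself is readable and consistent in Table 4 and Sections 6.2.1, 6.3.1, 6.5.1 and 6.5.2.
- **Importance.** No readable decision rule uses these parameters, and durvalumab is given at a fixed dose. This stands, and keeps the point to a low-cost improvement.

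**Conclusion.** The point holds conditionally. If the durvalumab terminal half-life exceeds about 11 days (10.5 by span, 11.6 by extrapolation, on a 27-day profile), Cycle 1 leaves more than 20% of AUC to infinity extrapolated and a fit under two half-lives long. Individual t1/2 and Vz are then imprecise and possibly biased low; CL is less affected. If C2D1 is not pre-dose, the limits fall to 7.0 and 8.6 days.

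This rests on an assumed half-life, on conventional limits, and on assumed error and distribution models. The 11.6-day limit is for one exponential; in the two-compartment simulation median extrapolation reaches 20% at about 14 days. The point concerns a secondary endpoint in Stage 1 only. Cmax, interval AUC and troughs remain usable, and the primary response-rate analysis is untouched.

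**What to change.** 1. **Protocol Section 6.5.1 and Table 4:** assay durvalumab in the Stage 1 serum already drawn for daratumumab PK at EOT, 28 days after EOT and 90 days after the last dose, if the volume allows (the documents give none). Estimate terminal t1/2 from those samples, using actual time since the last durvalumab dose. Sections 6.2.1 and 6.3.1 should then name both drugs.
2. **SAP Section 11.8:** report Cycle 1 Cmax, AUC over the dosing interval and trough for all subjects. Either summarise CL, Vz and t1/2 only where extrapolated AUC is at most 20%, or estimate them with a model that pools Cycle 1, trough and post-treatment samples. Late samples alone repair t1/2 only; CL and Vz need this step. Under the 20% rule, give the number of subjects excluded, because it keeps those with shorter estimated half-lives. The pooled model avoids that selection.
3. **Section 6.5.1:** state that the durvalumab samples on C2D1 and later are pre-dose.

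Cost: 3 assays × 18 subjects = at most 54, with no added visit or blood draw; one table row and a few sentences. The downside is a small assay cost, and some subjects will miss the late samples.
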